## 5. DEFINITIONS

### 5.1. Analysis Dates

#### 5.1.1. Study Start Date

For a subject who have had study procedure attempted, the study start date is defined as the procedure date.

#### 5.1.2. Treatment Start Date

The treatment start date is defined as the procedure date.

#### 5.1.3. Last Information Date

The last information date is defined as the latest date assessed with any available information concerning the subject (e.g., most recent date out of: baseline assessment, procedure, discharge, all follow-up visits, laboratory tests, study termination, and adverse events). Last information date is used as censor date for survival analyses.

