7.8.7.10 Withdrawal, Missed Visit, and Loss to follow-up

The Investigator will make every attempt to follow the patients at each of the required assessment periods. Patients may be withdrawn from the study for the following:

- **Patient Withdrawal**

The patient may voluntarily withdraw from the clinical study at any time, without penalty or loss of benefits to which they are otherwise entitled.

- **Physician Withdrawal**

The Principal Investigator also has the right to withdraw a patient if they feel it is in the best interest of the patient to do so.

- **Missed Visit / Lost to Follow-up**

If a patient cannot be reached for a follow-up visit, the Investigator will document the contact efforts made to the patient and/or effort to obtain hospital records in the appropriate electronic case report form. If the patient cannot be reached in any way, or misses a visit, the patient will be considered "missed visit" for that time interval. After two

documented unsuccessful attempts to schedule follow up visits sequentially (e.g., 1 year and 2 year follow-up), the patient will be considered “lost to follow-up.”

In all cases of withdrawal (as described above), withdrawn patients will not undergo further study follow-up procedures after the time of study exit. A study patient that has been withdrawn from the study will not be replaced.

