## 6. STATISTICAL ANALYSES

### 6.1. General Considerations

a. For continuous variables, summary statistics will include number of observations, mean, median, standard deviation, minimum, maximum, and 95% confidence intervals (based on normal distribution, unless otherwise specified) per table shells.

b. For categorical variables, summary statistics will include counts, percentages, and 95% Clopper-Pearson confidence intervals per table shells. In general, the denominator for the percentage calculation will be based on total number of subjects with evaluable data for a specified time point unless otherwise specified. Subjects with missing data will be excluded from the denominator.

c. Survival analysis techniques will be used to analyze the time-to-event variables. Summaries will include the number of subjects at risk, number of events, and number of subjects with the event. Subjects without events will be censored at their last known event-free time point. If this event-free time point occurs after the analysis time point, the days to event variable will be set equal to the analysis time point so that the subject will be included in the analysis. For subjects who did not have an event or early withdrawal and have not yet completed the analysis visit, they will be censored at their last information date. Time to first event curves will be constructed using Kaplan-Meier estimates and all post procedure results will be summarized with Kaplan-Meier estimates of event rates. Hazard ratios, confidence interval for the hazard ratios, and p-values may also be presented from a Cox proportional hazards model.

d. Descriptive statistics will be provided at each follow-up assessment, including change from baseline to subsequent time point for selected endpoints. Paired (i.e., subjects with available data at both baseline and respective time point) and unpaired data will be presented separately.

e. If insufficient data are available for summary statistics, then data will be provided only as listings.

f. Unless otherwise specified, descriptive analysis will be performed for all data. Nonparametric techniques may be used if the data does not meet the assumptions of parametric tests.

g. All analyses will be performed using SAS® Software version 9.4 or later (SAS Institute, Inc., Cary, NC).

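### SAP 5.1.3 and 6.1c give conflicting censoring rules, so a patient lost to follow-up can be credited with unobserved event-free time in the long-term mortality estimates

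*SAP*

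**What the plan says.** SAP 5.1.3 defines the last information date as "the latest date assessed with any available information concerning the subject". The examples it lists run from the baseline assessment through "procedure, discharge, all follow-up visits, laboratory tests, study termination, and adverse events". It then states: "Last information date is used as censor date for survival analyses". No exception is made by endpoint or by reason for leaving the study.

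SAP 6.1, item c, gives another rule: "Subjects without events will be censored at their last known event-free time point". It assigns the last information date to a narrower group: "For subjects who did not have an event or early withdrawal and have not yet completed the analysis visit". Event-free time that runs past the chosen horizon is cut back: "the days to event variable will be set equal to the analysis time point so that the subject will be included in the analysis".

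Protocol 7.8.7.10 treats a patient as lost after two "documented unsuccessful attempts to schedule follow up visits sequentially (e.g., 1 year and 2 year follow-up"). Protocol 7.8.7.11 makes loss to follow-up a study exit but does not say what date that exit carries.

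The SAP assigns Kaplan-Meier to the 30-day MAE composite (6.3) and to all-cause mortality at 30 days, 6 months, 1 year and annually thereafter (6.4).

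**The concern.** A Kaplan-Meier estimate is sound only if each patient counted at risk would have had an event recorded had one occurred. A lost patient censored at an administrative termination date stays in the denominator after last contact, when no event could be seen. Deaths then come only from patients still followed, while the risk set includes people nobody is watching, and the event rate is biased downward.

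The two SAP sections lead a programmer to different dates for the same patient. Section 6.1c does not settle the matter alone. It diverts lost patients from the last information date only if loss counts as early withdrawal, a term the SAP does not define. The protocol points both ways:

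- Section 7.8.7.10 places loss to follow-up among the withdrawal categories.
- Section 7.8.7.11 lists withdrawal and loss as separate exits.
- Section 17 defines subject withdrawal as a subject's own decision, which does not describe a lost patient.

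The last known event-free time point also has no date definition. The only censor date defined in SAP 5.1 is the last information date.

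**Working it through.** The documents give no loss rate, design event rate or figure for this point, so there is nothing to reproduce. The check has three parts.

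**1. Length of the unobserved interval.** Inputs are the visit windows in SAP 5.2. Assumption: termination is dated at the second consecutive missed visit.

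- Last seen at 6 months, 1- and 2-year visits missed (the protocol's own example of missed visits): 730 − 180 = 550 days. Across the windows, 685 − 210 = 475 to 775 − 150 = 625 days.
- Last seen at 30 days, 6-month and 1-year visits missed: 365 − 30 = 335 days (283 to 387).
- Last seen at 1 year, 2- and 3-year visits missed: 1095 − 365 = 730 days (640 to 820).

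If termination is dated at last contact, each of these is zero.

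**2. Effect on 2-year mortality.** Let annual mortality be *m* with constant hazard, so S(t) = (1 − m)^t. Assume a proportion *p* of those alive at 6 months is lost then, has the same hazard as the rest, has no later status recovered, and is kept in the risk set to 2 years. Then

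- true 2-year mortality = 1 − S(2);
- estimated survival = S(0.5) × [p + (1 − p) × S(1.5)];
- understatement = p × [S(0.5) − S(2)].

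Mortality of 5% a year is the figure in Protocol 3.3 for symptomatic severe MR. Six percent is the 1-year mortality in the randomized trial cited in Protocol 3.4.3.3. The values of 10-20%, and all loss rates, are assumptions.

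| Annual mortality | S(0.5) − S(2) | True 2-year | Understatement at 5% / 10% / 15% lost (points) |
|---|---|---|---|
| 5% | 0.9747 − 0.9025 = 0.0722 | 9.75% | 0.36 / 0.72 / 1.08 |
| 6% | 0.9695 − 0.8836 = 0.0859 | 11.64% | 0.43 / 0.86 / 1.29 |
| 10% | 0.9487 − 0.8100 = 0.1387 | 19.0% | 0.69 / 1.39 / 2.08 |
| 15% | 0.9220 − 0.7225 = 0.1995 | 27.75% | 1.00 / 1.99 / 2.99 |
| 20% | 0.8944 − 0.6400 = 0.2544 | 36.0% | 1.27 / 2.54 / 3.82 |

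At 15% annual mortality, for example, the estimate is 26.8%, 25.8% or 24.8% against a true 27.8%.

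**3. Finite-sample check with N = 60.** If *L* patients are lost before *E* events occur, censoring at last contact gives E/(60 − L), and censoring at termination gives E/60.

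- L = 3, E = 6: 6/57 = 10.53% against 10.00%.
- L = 6, E = 12: 12/54 = 22.22% against 20.00%.
- Over L = 1 to 9 and E = 3 to 12, the shift is 0.08 to 3.53 points.

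For 30-day MAE, the cut-back to the analysis time point limits the credit to at most about 30 days per patient, and only patients lost before day 30 matter. With 1 to 3 such patients and 3 to 6 events, the shift is 3/59 − 3/60 = 0.08 to 6/57 − 6/60 = 0.53 points.

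**The case against.** The strongest reply is that 6.1c is the operative rule and is sound. It censors at the last known event-free time and appears to keep the last information date for patients still in follow-up. With Protocol 7.8.7.10, which groups loss with withdrawal, lost patients would never receive a termination date and the bias would be zero. The definition in 5.1.3 also asks for a date with available information, and an exit date on which nothing was learned arguably does not qualify. For patients who complete, die or withdraw in person, the termination date usually does carry information, so listing it is not in itself an error. Protocol 7.8.7.10 and 10.5 also call for efforts to obtain hospital records and to contact the primary care provider, which may recover some status.

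Much of this stands. A reader might infer that the plan does credit every lost patient with unobserved time. The documents do not support that: it requires 5.1.3 to prevail, or loss to fall outside early withdrawal, and it requires termination to be dated well after last contact. None of these is stated. What the reply cannot do is remove the unrestricted sentence in 5.1.3 or supply the missing definition.

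Two further inferences go too far. Later MAE is assigned to counts and percentages in SAP 6.4, although 6.1c also speaks of Kaplan-Meier for all post-procedure results, so an effect there is uncertain. Inflated exposure in the linearized or Poisson rates is not established either: 5.1.3 ties the date to survival analyses, and no Poisson offset is specified.

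On size, the study is descriptive, with no test of mortality. The binomial standard error of a 9.75% rate in 60 patients is √(0.0975 × 0.9025/60) = 3.8 points, larger than the bias at 5-6% mortality. But bias in a known direction does not shrink with more patients, and the confidence interval does not reflect it.

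**Conclusion.** The concern holds as a conflict between two stated censoring rules, one of which can bias Kaplan-Meier event rates downward if applied as written. The main exposure is long-term all-cause mortality. At 2 years the understatement is about 0.4 to 1.3 points with the 5-6% mortality the protocol cites and 5-15% lost, and 0.7 to 3.8 points if annual mortality is 10-20%.

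These sizes assume that all losses occur at the 6-month visit, that no later status is recovered, that the lost share the hazard of the rest, and that termination is dated at the second missed visit. Under the alternative readings described above the bias is zero. The 30-day primary safety endpoint would move by about half a point or less in the cases with up to 3 lost and 6 events.

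**What to change.** Make 5.1.3 agree with 6.1c under a single rule:

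- For all-cause mortality, censor at the last date the patient was known to be alive.
- For other time-to-event endpoints, censor at the last contact at which those events were assessed. A stray laboratory date does not establish freedom from every MAE component.
- Exclude the study-termination date for lost or withdrawn patients unless status was ascertained on that date.
- State that loss to follow-up is handled as early withdrawal.

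The cost is SAP wording and the matching derivation of the censor date, with no new data collection. The change removes the unobserved time. It does not correct for lost patients having a different risk from those followed.

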### 5.2. Visit Windows

The follow-up schedule and analysis windows are listed below.

- Post implant (within 24 hrs)
- Discharge visit (discharge or 7 days post-procedure, whichever comes first)
- 30-Day Visit  $\pm$  7 Days [23, 37 days]
- 6-Month Follow-up (180  $\pm$  30 days) [150, 210 days]
- 12-Month Follow-up (365  $\pm$  45 days) [320, 410 days]
- 2 years (730 days)  $\pm$  45 days [685, 775 days]
- 3 years (1095 days)  $\pm$  45 days [1050, 1140 days]

- 4 years (1460 days)  $\pm$  45 days [1415, 1505 days]
- 5 years (1825 days)  $\pm$  45 days [1780, 1870 days]

## 6. STATISTICAL ANALYSES

### 6.1. General Considerations

a. For continuous variables, summary statistics will include number of observations, mean, median, standard deviation, minimum, maximum, and 95% confidence intervals (based on normal distribution, unless otherwise specified) per table shells.

b. For categorical variables, summary statistics will include counts, percentages, and 95% Clopper-Pearson confidence intervals per table shells. In general, the denominator for the percentage calculation will be based on total number of subjects with evaluable data for a specified time point unless otherwise specified. Subjects with missing data will be excluded from the denominator.

c. Survival analysis techniques will be used to analyze the time-to-event variables. Summaries will include the number of subjects at risk, number of events, and number of subjects with the event. Subjects without events will be censored at their last known event-free time point. If this event-free time point occurs after the analysis time point, the days to event variable will be set equal to the analysis time point so that the subject will be included in the analysis. For subjects who did not have an event or early withdrawal and have not yet completed the analysis visit, they will be censored at their last information date. Time to first event curves will be constructed using Kaplan-Meier estimates and all post procedure results will be summarized with Kaplan-Meier estimates of event rates. Hazard ratios, confidence interval for the hazard ratios, and p-values may also be presented from a Cox proportional hazards model.

d. Descriptive statistics will be provided at each follow-up assessment, including change from baseline to subsequent time point for selected endpoints. Paired (i.e., subjects with available data at both baseline and respective time point) and unpaired data will be presented separately.

e. If insufficient data are available for summary statistics, then data will be provided only as listings.

f. Unless otherwise specified, descriptive analysis will be performed for all data. Nonparametric techniques may be used if the data does not meet the assumptions of parametric tests.

g. All analyses will be performed using SAS® Software version 9.4 or later (SAS Institute, Inc., Cary, NC).

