9.3 Statistical Analysis

A first analysis will be performed when 30 patients complete 30-day follow-up, and a second analysis when all patients in the primary cohort complete their 30-day follow-up. A pooled analysis of all patients from the primary cohort and additional cohort will also be performed. Descriptive statistics will be presented for all primary and secondary endpoints. For quantitative variables, the mean values, standard deviation, maximum and minimum will be calculated. The 95% confidence interval (CI) for the mean will be calculated when relevant.

For qualitative variables, absolute and relative frequencies are determined. Exact binomial 95% confidence interval for proportions will be calculated when relevant.

For combined and individual clinical endpoints the survival rate (and 95% CI) will be calculated using Kaplan-Meier estimator. Kaplan-Meier survival curves will also be presented when relevant.

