### 2.2. Study Design

This is a multi-center (up to 20 sites), multi-national, prospective, single arm study. The analysis population will consist of 60 patients. No site will be allowed to enroll more than 20% of the analysis population. All enrolled study patients will be assessed for clinical follow-up at the following intervals: 30 days, 6 months, 1 year and annually for 5 years post implant procedure. In addition, the study allows for 0 to 3 roll-in patients per site where allowed, for a total maximum of 60 roll-in patients. The overall study therefore allows for up to 120 patients: 60 in the analysis population, and up to 60 additional roll-in patients.

Of the total enrollment, 45 patients will be enrolled in the U.S. at up to 9 clinical sites. In the event that the 60-patient analysis cohort fills prior to the completion of the US EFS cohort, the US EFS cohort may continue to enroll until completed.

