#### 4. ANALYSIS POPULATIONS

- **Intent-to-treat population**

The intention-to-treat (ITT) population includes all patients in whom the study procedure has been attempted (i.e., incision). The ITT population does not include roll-in patients.

- **Per-protocol population**

The per-protocol (PP) population includes all patients in the ITT population in whom the study device was introduced in the body, and do not have any major protocol deviations.

- **Implanted population**

The implanted population includes all patients in whom the study device was implanted in the body at the time of the patient's exit from the cardiac catheterization laboratory.

- **Roll-in population**

Up to three roll-in patients per site may be allowed, but not required (e.g., for sites with sufficient prior experience with the system). The study Sponsor will review each situation to determine when a site may start enrolling in the ITT population.

The PP population will be the primary analysis population for performance and safety assessment. The ITT population will be used for additional safety analysis. Additional analyses of performance and safety data using the implanted population will be performed if it is clinically meaningful in addition to the PP analysis. Subgroup analysis by etiology may be performed. For patients with mixed etiology, the echo core lab will determine the dominant etiology for analysis. All analyses will be performed separately for the roll-in population.

A first analysis will be performed when 30 patients complete 30-day follow-up, and a second analysis when all patients complete their 30-day follow-up.

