#### 6.4. Analyses of Secondary Endpoints

Mitral regurgitation reduction from baseline at 30 days, 6 months, 1 year and annually thereafter will be summarized with counts and percentages.

All-cause mortality rates at 30 days, 6 months, 1 year, and annually thereafter and corresponding 95% confidence intervals will be computed using the Kaplan-Meier algorithm with the standard errors being computed using Greenwood's formula.

Recurrent heart failure hospitalization at 30 days, 6 months, 1 year, and annually thereafter will be analyzed using Poisson regression.

Re-intervention rates for mitral regurgitation at 30 days, 6 months, 1 year and annually thereafter will be summarized with counts and percentages.

Composite of major adverse events (MAE) defined as cardiovascular mortality, stroke, myocardial infarction, new need for renal replacement therapy, severe bleeding and re-intervention for study device related complications at 6 months, 1 year and annually thereafter will be summarized with counts and percentages.

Change from baseline in Left Ventricular End Diastolic Volume (LVEDV), Left Ventricular End Systolic Volume (LVESV), Pulmonary Artery Systolic Pressure, 6MWT distance, BNP/NT-pro-BNP level, effective regurgitant orifice area (EROA) and mitral regurgitant volume at the protocol specified timepoints in the secondary endpoints and clinical outcomes section will be summarized by mean and standard deviation for the PP population. For the analyses of six minute walk test (6MWT), subjects unable to perform the walk due to a medical reason will be considered to have walked an actual distance of zero.

Change from baseline in Quality of Life (QoL) score, as measured by Kansas City Cardiomyopathy Questionnaire (KCCQ), and EQ5D at 30 days, 6 months and 1 year and annually thereafter will be

summarized by mean and standard deviation. Patients that are missing a baseline or follow up values will be excluded from the analysis.

Change from baseline in NYHA Functional Classification at 6 months, 1 year and annually thereafter will be presented as shift from baseline for each of the pre-specified follow-up periods. Subjects that are missing a baseline or follow-up values will be excluded from the paired analysis.

Change from baseline in tricuspid regurgitation at 6 months, 1 year and annually thereafter will be summarized with counts and percentages.

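### SAP 6.1(a) bases the default confidence interval for a mean on the normal distribution; if that means a 1.96 multiplier, intervals are slightly too narrow, and the text should name the t distribution

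*SAP*

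**What the plan says.** SAP 6.1(a) lists the summary statistics for continuous variables and ends with "95% confidence intervals (based on normal distribution, unless otherwise specified", then refers to the table shells. SAP section 10 places those shells in a separate second part of the SAP. Protocol 9.3 says "The 95% confidence interval (CI) for the mean will be calculated when relevant" and names no distribution, so SAP 6.1(a) is the only visible rule for the interval of a mean.

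The sample sizes to which the rule applies are set out as follows:

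- SAP 2.2: "The analysis population will consist of 60 patients", with roll-in patients in addition, "for a total maximum of 60 roll-in patients".
- SAP 4: "A first analysis will be performed when 30 patients complete 30-day follow-up".
- SAP 4, on roll-ins: "All analyses will be performed separately for the roll-in population".
- SAP 4, on etiology: "Subgroup analysis by etiology may be performed". Mixed cases are assigned a dominant etiology by the echo core laboratory.

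For the change from baseline in LV volumes, 6MWT, BNP, EROA and similar measures, SAP 6.4 says only that they "will be summarized by mean and standard deviation for the PP population". Any interval for them comes from the general clause in 6.1(a).

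**The concern.** The standard deviation is estimated from the same patients as the mean. For normal data, the multiplier that gives 95% coverage is then the t quantile with n-1 degrees of freedom, and 1.96 is its large-sample limit. Elsewhere the SAP names its interval methods: Clopper-Pearson for proportions and Kaplan-Meier with Greenwood standard errors for mortality. Next to these, a reference to the normal distribution reads most directly as naming a method too, namely a z multiplier. On that reading proportions get an exact small-sample interval while means get a large-sample one, in a study that first reports at 30 patients.

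What is at stake is modest. One stated objective is to guide the design of later studies. An interval for a mean change that is too narrow overstates how well that change is known, and more so as n falls. A programmer working from the visible text could also choose either quantile, a choice that an SAP should close.

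**Working it through.** The documents give no interval width, power or sample size that depends on this quantile, so there is no figure of the plan to reproduce except the nominal 95%. The check compares that level with what each multiplier delivers.

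**Inputs.** Level 95%, two-sided (SAP 6.1(a)). n=30 at the first analysis (SAP 4). n=60 in the analysis population (SAP 2.2). Roll-in 0 to 60 (SAP 2.2). The sizes of the etiology groups, the actual roll-in set and the late-visit sets are not stated; n from 5 to 20 is assumed below to show the range. No standard deviation is needed, because it cancels.

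**Formulas**, for normal data with an estimated SD:

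- Literal reading: mean ± 1.960 × SD/√n
- t interval: mean ± t(0.975; n-1) × SD/√n
- Coverage of the literal interval = 2 × F(1.960; n-1) - 1, where F is the t distribution function
- Shortfall in width = 1 - 1.960 / t(0.975; n-1)

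**Results**

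| n | Status of n | t multiplier | Literal interval too narrow by | Coverage of literal interval |
|---|---|---|---|---|
| 60 | stated | 2.001 | 2.1% | 94.5% |
| 30 | stated | 2.045 | 4.2% | 94.0% |
| 20 | assumed | 2.093 | 6.4% | 93.5% |
| 15 | upper bound, see below | 2.145 | 8.6% | 93.0% |
| 10 | assumed | 2.262 | 13.4% | 91.8% |
| 5 | assumed | 2.776 | 29.4% | 87.8% |

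For example, at n=30 the shortfall is 1 - 1.960/2.045 = 4.2%, and the half-width goes from 1.960/√30 = 0.358 SD to 2.045/√30 = 0.373 SD. At n=60 it goes from 0.253 SD to 0.258 SD.

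**The n=15 row.** If the optional etiology analysis is run on the first 30 patients, and each is classed as functional or degenerative, the smaller group has at most 30/2 = 15 patients. Missing values are not imputed (SAP 6.2) and changes need both values (SAP 6.1(d)), so its n can only be lower. The shortfall there is at least 8.6% and coverage at most 93.0%. In the full 60 the smaller group has at most 60/2 = 30, so the shortfall is at least 4.2%.

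**If t is used**, coverage is 95% at every n for normal data. If the SAP already means t, the shortfall column is zero throughout.

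**The case against.** The strongest objection is that the wording does not fix a z quantile. The SAP never prints 1.96 and never treats the SD as known. A t interval also rests on the normal distribution of the data, and item (f) of the same section contrasts parametric with nonparametric techniques, so the parenthesis may only state the distributional assumption. It is also a default that can be overridden, and it defers to shells that are not available. All of this stands. A reader might infer that the plan as printed produces intervals that are too narrow; the documents support this only on the literal reading.

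A reader might also infer that the roll-in, etiology and late-visit analyses are badly affected. The documents do not show these sets to be small. Roll-in can reach 60, the etiology analysis is optional, and late-visit numbers are not given. SAP 6.1(e) sends insufficient data to listings, though without a threshold. Only the bound of 15 for the first 30 patients follows from stated figures, and it depends on the optional analysis being done at that time.

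Nor are these the only intervals in the study. The SAP also has Clopper-Pearson and Greenwood intervals, Poisson regression, optional Cox models and a Fisher test for poolability. The primary safety endpoint uses Kaplan-Meier, and the performance endpoints use counts and percentages. The 6MWT and LV-volume endpoints begin at 6 months, so they are not due at the 30-day trigger. Of the continuous secondary endpoints, KCCQ, EQ5D, EROA and regurgitant volume are.

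Finally, the coverage figures assume normal data. 6MWT is set to zero for patients medically unable to walk, and BNP need not be normal, so a t multiplier would not guarantee 95% there.

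These objections limit the point but do not remove it. The only visible rule leaves the multiplier open, and its most direct reading is the less accurate one.

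**Conclusion.** A minor point of wording that is worth correcting. On the literal reading, with an estimated SD and normal data, the default interval is about 2% too narrow in the 60-patient population and 4% at the 30-patient analysis, or 0.5 and 1.0 percentage points of coverage. It is at least 8.6% too narrow in the smaller etiology group if the first 30 patients are split. The 13% and 29% figures are illustrations at assumed sizes of 10 and 5. If the phrase means normal theory with a t quantile, or the shells say so, the shortfall is nil. No primary endpoint, hypothesis test or sample size changes on either reading.

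**What to change.** In SAP 6.1(a), replace the parenthesis with: *based on the t distribution with n-1 degrees of freedom, unless otherwise specified*. Make the table shells match, so that text and programming cannot differ. Protocol 9.3 needs no change, since it names no distribution.

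The cost is one phrase. Compared with a 1.96 multiplier, intervals widen by about 4% at n=30 and 2% at n=60. If t was always intended, no result changes and the text becomes unambiguous.
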